- Précis:** Pilot trial designed with a two part aim at enrollment. Aim 1 is designed as a randomized, controlled trial for older patients (≥ 75 years) who are indicated for CRT device implantation to receive a CRT-P or CRT-D. Information collected will help to assess the ability to enroll and retain older patients in a randomized controlled trial of CRT-P versus CRT-D in preparation for a large pivotal trial. Aim 2 is a non-randomized, observational study of patients who were offered inclusion into Aim 1 but refused to participate. Aim 2 subjects present an opportunity to understand the reasons why older patients may refuse enrollment into a randomized trial as well as still allowing for collection of data regarding their chosen CRT device.
- Objectives:** **Primary Objective:** Feasibility of enrolling and maintaining elderly heart failure patient in CRT-P vs CRT-D randomized trial.
Secondary Objectives: Examine predictors of refusing randomization and of choosing CRT-P vs. CRT-D device implantation in elderly patients.
- Endpoint** **Primary Endpoint:** The ability to enroll in the randomized controlled trial of CRT-P versus CRT-D patients.
Secondary Endpoints: Determinants of refusing participation in CRT-P versus CRT-D clinical trial.
- Population:** Patients 75 years or older who are clinically indicated for CRT device implantation based on published guidelines⁶ will be considered for this trial. The racial, gender, and ethnic characteristics of the proposed subject population represent the populations cared for at the participating institutions. Subjects meeting all inclusion and none of the exclusion criteria for Aims 1 and 2 will be enrolled in this research. No exclusion criteria shall be based on race, gender, or HIV status. Patients younger than 75 years of age are excluded based on study rationale and design.
- Study Type:** Pilot trial with two clinical Aims. Aim 1 is a randomized clinical trial and Aim 2 is an Observational clinical trial.
- Number of Sites**
Enrolling Participants: Total of four participating sites
- Study Duration:** Approximately 24 months
- Participant Duration:** Up to 18 months from enrollment

2 INTRODUCTION: BACKGROUND INFORMATION AND SCIENTIFIC RATIONALE

2.1 BACKGROUND INFORMATION

Heart failure (HF)¹⁻⁵ is a disease of epidemic proportions in the United States affecting over 5 million individuals. While the incidence of many diseases in the U.S. is decreasing, HF represents one of only two human diseases that are increasing in frequency. It is estimated that nearly 400,000 new cases of HF will be diagnosed in the next year, one million patients will be hospitalized, and 300,000 patients will die from HF in the U.S. Although the development of new medications has substantially broadened the therapeutic armamentarium over the past decades, the long-term prognosis for patients with HF remains poor with less than 50% of patients surviving five years after the initial diagnosis. A characteristic feature of HF is that it is a progressive disease with patients having repeated and progressively more frequent hospitalizations for worsening symptoms. HF puts an overwhelming burden on patients as evidenced by dramatically diminished quality of life (QOL). It also has a marked impact on the economics of our health system accounting for over 50 billion dollars in annual national healthcare expenditure.

Cardiac resynchronization therapy (CRT) is an established therapy in HF⁶. HF patients with severe cardiomyopathy and ventricular conduction abnormalities, as demonstrated by a wide QRS waveform on surface electrocardiogram (>120 ms), who continue to suffer from HF symptoms (New York Heart Association Classes II, III, and ambulatory IV) despite optimal pharmacological therapy

including angiotensin converting enzyme inhibitors/angiotensin receptor blockers, β -blockers, and potassium-sparing diuretics can benefit from CRT with improved maximum oxygen consumption, exercise tolerance, and improved QOL^{7,8}. Results of large, multicenter, randomized controlled trials such as *Companion*⁹ and *Care-HF*¹⁰ demonstrate, in addition, a significant decrease in the composite endpoint of death or HF hospitalization with CRT over optimal pharmacological therapy. Studies also suggest a benefit of CRT on reducing the burden of ventricular arrhythmias¹¹. It is estimated that about 40% of patients who have systolic HF are CRT candidates by current guideline criteria⁶.

CRT-P versus CRT-D

CRT can be delivered through a pacemaker (CRT-P) or a defibrillator (CRT-D). CRT-P devices are smaller (i.e. require a smaller surgical incision at implantation) and cost a fraction of the price of CRT-D devices. Both CRT-P and CRT-D provide resynchronization to the failing heart through low energy pacing impulses, but CRT-D can additionally deliver high-energy shock therapy to terminate life-threatening ventricular arrhythmias. Compared to optimal pharmacological treatment, both CRT-P and CRT-D have been shown in randomized controlled trials^{9,10} to reduce all-cause mortality and improve patient symptoms and cardiac function. In one study comparing them to each other⁹, CRT-P and CRT-D had equivalent benefits in reducing the composite endpoint of death or HF hospitalization⁹. For the endpoint of all-cause mortality however, CRT-D exhibited a non-significant trend towards lower mortality compared to CRT-P when considering HF patients of all ages⁹. Published guidelines do not distinguish between the clinical indications for CRT-P and CRT-D⁶.

High Energy Defibrillator Therapy is Non-Specific

High energy defibrillator shocks are non-specific i.e. most defibrillator recipients never receive shock treatments. Of 100 patients implanted with a defibrillator for primary prevention, ~23% receive appropriate shocks in response to life-threatening ventricular arrhythmias over long term follow-up¹². In addition, it is estimated that about 4 appropriate defibrillator shocks account for one life saved^{13, 14}. Moreover, defibrillators may deliver inappropriate therapy¹⁵ and may have significant short and long term complications¹⁶ thus negatively impacting QOL. Shocks are painful, drain device battery, and add significantly to the cost of care for patients because of a higher burden of visits to the emergency department or outpatient clinics as well as admissions to the hospital and surgical procedures for replacement of depleted device batteries. In addition, the number of defibrillators and defibrillator lead malfunctions resulting in advisories and recalls by the Food and Drug Administration have increased significantly over the past decade¹⁷ out of proportion to those seen with the simpler pacemaker devices, thus adding to the morbidity and mortality of defibrillator recipients and to the overall cost of health care.

CRT in the Elderly

The U.S. and Europe populations are getting older. For instance, in the United States, the population aged 80-84 years increased by 16.1%, and those aged 85-89 years increased by 29.8% from 2000 to 2010¹⁸. Although not excluded from the large CRT randomized trials^{9, 10}, older patients (≥ 75 years) have been largely underrepresented in these trials but still receive up to 40% of all CRT-D's in the United States^{19,38}. Moreover, older patients have a higher risk of death than younger patients based on competing causes of death and comorbid conditions, thus stirring controversy regarding the role of defibrillator therapy in the elderly²⁰⁻²⁴. In addition, data from large CRT-D registries show that the odds of receiving appropriate defibrillator shocks decrease significantly with every decade of age²⁵.

Potential Impact

A large, randomized, non-inferiority trial comparing mortality and QOL in older HF patients receiving CRT-P versus CRT-D therapy addresses a critical clinical practice area. Uncertainty about the comparative outcomes of older patients with these two therapies leads to suboptimal and costly management of HF: Older CRT recipients often receive the larger and more expensive CRT-D device that can deliver painful shocks, in the absence of any proof for incremental survival benefit with CRT-D over CRT-P. The pilot randomized trial of this proposal (Aim 1) will be essential to the design of a large pivotal trial. This project will also have significant scientific impact because it will evaluate the clinical and demographic predictors of choosing CRT-P or CRT-D therapy as well as patients' change in their satisfaction with their decision 6 months after enrollment. The results of this research will ultimately effect clinical change in the management of elderly CRT recipients driven by changes to the CRT published guidelines. This research is likely to impact clinical practice and will be important to many stakeholders, including elderly patients and their families, physicians, hospitals, and third party payers, especially Medicare.

2.2 RATIONALE

Since the initial introduction of the defibrillator as a life-saving therapy almost 30 years ago, most large scale clinical trials^{9, 10, 12-16} have focused on expanding its clinical indications by identifying newer patient groups at increased risk of sudden cardiac death that may benefit from this therapy. From the original surgically-implanted single-chamber 'shock box' devices used in survivors of cardiac arrest, the field moved steadily in the direction of expanding the indications to larger patient groups. Today, defibrillators are implanted mainly for primary prevention of sudden cardiac death in patients with low left ventricular ejection fraction ($\leq 35\%$) who have never experienced a life-threatening arrhythmia^{13, 14}. They are also implanted in HF patients, a significant proportion of whom requires CRT devices^{9, 10}. Driven by industry sponsors, on-going trials are now investigating the role of the implantable defibrillator in patients with relatively preserved ventricular function (ejection fraction between 36% and 50%)²⁶ who never had ventricular arrhythmias. Yet, despite the established benefits of defibrillator therapy on survival, few patients implanted with these devices receive electrical treatment from them¹⁹.

The proposed research is innovative because it takes a perspective that goes in the opposite direction to most studies of the past 3 decades that have aimed to expand the indications for defibrillator therapy. Instead, our project investigates whether in a subset of patients (age ≥ 75 years) who are currently indicated for CRT device implantation, the smaller, simpler, and cheaper CRT-P is equivalent to the CRT-D in decreasing mortality and improving QOL. Of note, the proposed patient population overwhelmingly receives CRT-D therapy in the U.S. today ($>80\%$ of cases)²⁷, presumably because of an overinflated estimate of the protective role of defibrillator therapy in these patients, which is based on results extrapolated from other non-CRT trials, which were performed in different patient populations¹³⁻¹⁵. As opposed to studying the eligibility of non-indicated patients to receive an available therapy with the goal of expanding its clinical indications, we propose to study a subgroup of patients that is currently indicated for CRT-D therapy according to the published national guidelines⁶ and CMS reimbursement policies²⁸ but is poorly represented in large randomized trials¹⁴ and is least likely to benefit from defibrillator therapy.

Our proposal is also important because it focuses exclusively on elderly patients who although not excluded from randomized trials of cardiac implantable electronic devices, have been grossly underrepresented in these trials^{9, 10, 12-16}. Elderly patients constitute a fast-growing stratum of the United States population and an important one given that the burden of cardiac disease and the cost of health care increase dramatically in the later years of life. To our knowledge, the proposed trial would be the first cardiac implantable electronic device trial to be performed exclusively in

patients 75 years of age or older, thus focusing on this large stratum of the population that is neglected in clinical cardiac research.

Finally, our research will create a cohort of patients who declined enrollment into the pilot randomized controlled trial. This observational cohort will provide an opportunity to examine the clinical and demographic determinants of choosing CRT-P versus CRT-D in older HF patients. These decisions are typically made by the patients with help from caregivers and other family members, after discussing the pros and cons with the treating physician. We will also assess the patients' satisfaction with their decision to receive CRT-P versus CRT-D, at baseline and 6 months after enrollment. Examining the factors that predict patients' choice of CRT-P versus CRT-D in HF management and the level of satisfaction of patients is novel in the field of cardiac implantable electronic device management.

2.3 POTENTIAL RISKS AND BENEFITS

2.3.1 KNOWN POTENTIAL RISKS

For the Aim 1 randomized trial subjects, they will be screened for appropriateness of the trial before being randomized. If there is any indication that the patient should receive a CRT-D over a CRT-P then the patient will not be considered for the trial. Once the patient is enrolled in the Aim 1 the choice to have a randomized decision will not increase any health risks to the patient. Both the CRT-P and CRT-D device implantations are part of the standard medical care for HF patients. The risks involved with the implantation of either device are comparable to those of patients not enrolled in this research study. The risks include, but are not limited to, death, stroke, heart attack, damage to the heart or lungs or veins, infections, bleeding, arrhythmias, or the need for emergent open-heart surgery. These risks are the same in patients undergoing the CRT-P or CRT-D implantation procedures but who are not enrolled in this research study. Defibrillator devices include additional risk of shocks that can occur when there is an abnormal heart rhythm detected by the device. Occasionally, the device may deliver a shock for unintended reasons (a benign heart rhythm or noise).

For the observational Aim there is no additional health risk to the patients as only the patients' health information will be collected. There is a risk that the patients personal or health information may become exposed outside of the observational trial. This risk will be minimized by using all possible safeguards to help reduce risk of exposure. This risk also applies to the Aim 1 subjects.

2.3.2 KNOWN POTENTIAL BENEFITS

There may be no direct benefits to the subjects as a result of their participation in this study. The possible benefits of this procedure, using the pacemaker or the defibrillator, would be to help the subjects heart function in a more synchronized manner. By participating in this study, subjects may contribute valuable information to medical science that may benefit future patients with their same condition. The sponsor cannot guarantee any benefit to the subjects for their participation in this study.

3 OBJECTIVES AND PURPOSE

[figure not shown]
The primary objective is to evaluate and determine the feasibility of enrolling and maintaining elderly heart failure patients in the CRT-P versus CRT-D randomized trial. Additionally, for Aim 2, the observational arm will also maintain the same objective. Secondary objective is to examine the predictors of undergoing Pacemaker versus Defibrillator device implantation in elderly patients (≥ 75 years).

4 STUDY DESIGN AND ENDPOINTS

4.1 DESCRIPTION OF THE STUDY DESIGN

The design of this pilot study is in two parts corresponding to Aims 1 and 2 (Figure 1). Aim 1 is designed as a pilot randomized, controlled trial to be conducted at 4 institutions in the United States. It will randomize older patients (≥ 75 years) who are indicated for CRT device implantation to receive a CRT-P or a CRT-D. The choice of the design of Aim 1 was intended to mimic the design of a future large, multicenter, non-inferiority trial which would provide definitive answers regarding the relative impact of CRT-P versus CRT-D on total mortality and QOL in older patients. This specific design is necessary to allow the gathering of hard data on rates of screening of patients, acceptance of enrollment, randomization, device implantation, and patient retention during follow-up. Any design variations are likely to introduce biases which would increase the chances of flawed design of the pivotal trial.

Aim 2 is a non-randomized, observational study of patients who were offered inclusion into Aim 1 but refused to participate. We speculate that a majority of those patients who refuse participation in the randomized pilot trial do so because of a strong preference for CRT-P or CRT-D. This cohort complements Aim 1 and presents an opportunity to understand the reasons why older patients may refuse enrollment into a randomized trial of CRT-P versus CRT-D and to examine the demographic and clinical determinants associated with choosing a CRT-P versus a CRT-D device. It also provides the means to measure patients' QOL and satisfaction³²⁻³⁴ with decision (CRT-P or CRT-D), at baseline and 6 months after enrollment into this observational cohort.

4.2 STUDY ENDPOINTS

4.2.1 PRIMARY ENDPOINT

With the Aim 1 randomized subjects the primary endpoint is the ability to enroll in the randomized controlled trial of CRT-P versus CRT-D patients. The subjects enrolled with aid in determining and assessing feasibility of screening, enrolling, randomizing, and retaining participants in this pilot trial.

4.2.2 SECONDARY ENDPOINTS

The subjects enrolled in Aim 2 will help to determine the clinical and demographic characteristics of subjects who refused participation in the pilot randomized trial and to compare them to those in Aim 1. Therefore the secondary endpoint is the determination of predictors of refusing participation in CRT-P versus CRT-D clinical trial.

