5.3 OBSERVATIONAL SUBJECT ENROLLMENT

Patients identified in Aim 1 who refuse to participate will be offered to enroll in the observational cohort of Aim 2. Patients are eligible to enroll in the observational cohort at the time of implant through fourteen days' post procedure. There is a separate written, informed consent designed specifically for the prospective observational study. Sites are to collect, from all patients enrolled in Aim 2, their reason(s) why they refused enrollment in Aim 1. It is anticipated that a majority of these patients will accept participating in the observational study of Aim 2 that allows them to retain control over their decision.

The research coordinator at each site will maintain a detailed log of all patients who were offered participation in the non-randomized observational cohort, whether they signed a consent form or not. Reasons for declining participation in the research protocol of Aim 2 will be recorded. The inclusion and exclusion criteria for Aim 2 are identical to Aim 1.

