5.4 STRATEGIES FOR RECRUITMENT AND RETENTION

Patients presenting to the outpatient cardiology clinics or inpatient services of the 4 participating institutions and who are prescribed CRT device implantation or CRT-D device change-out for battery depletion will be considered for participation in this pilot randomized trial. The main investigator at each site will identify prospective patients who may require CRT device implantation. This will be achieved by screening the inpatient services and outpatient clinics of the cardiac electrophysiology services at each site. Research coordinators will verify that the prospective subjects meet all the inclusion and none of the exclusion criteria for the study. Once this information is ascertained, the investigator, research coordinator, or both will approach the patient to explain the rationale of the study and its requirements. After signing written informed consent, patients will be randomized to receive a CRT-P or a CRT-D device. Block randomization by enrolling site will be adopted. The randomization status of the patient will be communicated to the treating cardiologist. Of note, the surgical procedure for CRT-P or CRT-D implantation is similar with respect to duration and risk of the procedure, with the exception that CRT-D implantations require a larger skin incision (~1.5 inches versus 0.75 inches).

The research coordinator at each site will maintain a log of all patients who were screened for this pilot trial. The log should include reasons for why the patient did not meet either the inclusion or the exclusion criteria. Additionally, the log would also include the patient's reason for not wanting to enroll in the Aim 1 clinical trial. This log will be maintained at each individual site and redacted of identifiable information in order to send to the sponsor upon request. Use of patient initials and age will be used in place of patient's full name and date of birth.

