9.2 SAMPLE SIZE

Randomized Aim

It will be of interest to estimate the recruitment success rate and the retention rate in this population, as that will be useful knowledge for designing a pivotal non-inferiority trial. The proposed sample size of 50 patients guarantees a maximum sample standard deviation = $\sqrt{(.5*(1-.5)/50)} = 7\%$, meaning that a 95% confidence interval will have a maximum margin of error $\pm 13\%$ in estimating true retention rate. However, this margin-of-error may be lower (the further the sample retention is from 50%). For example, if 40/50=80% participants enrolled complete at least the 6-month visit, a 95% CI estimating the true 6-month retention in this population would range from 68.9-91.1%, information that can be used to guide recruitment estimates for the large scale trial. The recruitment success rate can be estimated with even more precision, as there will be a larger N approached than N enrolled (and thus a smaller standard deviation of the sample proportion).

Observational Aim

It is anticipated based on the physician and patient surveys that approximately 40% of patients offered the opportunity to enroll in the pilot randomized controlled trial of Aim 1 will do so. Therefore, 125 patients will need to be screened to enroll 50 in the pilot randomized trial. It is assumed that 80% of those who decline participation in Aim 1 will agree to be followed in the observational cohort, the cohort will consist of 60 non-randomized patients. A comparison will be scored on the Satisfaction with Decision Scale using a t-test (or Wilcoxon rank-sum test, if non-normally distributed). Assuming roughly equal numbers select CRT-D vs. CRT-P, enrollment of 60 cohort participants will have 80% power to detect a difference in Satisfaction with Decision scores if one treatment group's average score is at least 0.75 standard deviations higher than the other group.

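### Refusers of Aim 1 are described from those who then consent to Aim 2; on the plan's figures 15 of 75 enter no refusal analysis, although site logs are to hold their reason and age

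*Combined protocol and SAP*

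**What the plan says.** Section 4.2.2 names Aim 2 enrollees as the source for who refused: "The subjects enrolled in Aim 2 will help to determine the clinical and demographic characteristics of subjects who refused participation". They are to be compared with Aim 1, and the secondary endpoint is the set of predictors of refusing the trial. Section 9.3 repeats the contrast as Aim 1 against Aim 2 and calls learning who refuses, and why, the main purpose of Aim 2.

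Reasons are gathered from the same group. Section 5.3: "Sites are to collect, from all patients enrolled in Aim 2, their reason(s) why they refused enrollment in Aim 1".

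Section 9.2 does not expect all refusers to join: "It is assumed that 80% of those who decline participation in Aim 1 will agree to be followed in the observational cohort".

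Two logs reach further than the Aim 2 cohort:

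- The screening log in section 5.4 covers everyone screened. It is to include the patient's "reason for not wanting to enroll in the Aim 1 clinical trial", and it identifies patients by initials and age. On its use, section 5.4 says: "This log will be maintained at each individual site and redacted of identifiable information in order to send to the sponsor upon request".
- The log in section 5.3 covers everyone offered Aim 2, whether or not they consented, and reasons for declining Aim 2 are recorded.

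Section 9.1 gives neither log a part in the analysis of refusal. For people who do not enroll, it promises only the number approached. Its Observational Aim text compares CRT-P with CRT-D recipients.

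**The concern.** The endpoint concerns everyone who refuses Aim 1, but the data come from refusers who went on to give a second consent. Whether a refuser joins Aim 2 may depend on why Aim 1 was refused. Section 4.1 speculates that most refusers have a strong device preference. Section 5.3 expects most of them to accept Aim 2 because it leaves the device choice with them. If that is right, patients who refuse for other reasons may be under-represented in Aim 2, and nothing in the plan would show it.

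The pivotal trial's recruitment depends on this answer. Section 9.3 gives the example of making referring cardiologists site investigators if their opinion proves to be a major reason for refusal. A distorted mix of reasons could point to the wrong remedy, and a larger Aim 2 cohort would not correct it.

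**Working it through.** **Inputs, all from section 9.2.** Aim 1 acceptance: "approximately 40% of patients offered the opportunity to enroll in the pilot randomized controlled trial of Aim 1 will do so". Number needed: "125 patients will need to be screened to enroll 50 in the pilot randomized trial". Aim 2 uptake among refusers: 80%.

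**Step 1: reproduce the plan's figures.**

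- Offered Aim 1: 50 / 0.40 = 125, as stated.
- Refuse Aim 1: 125 − 50 = 75.
- Join Aim 2: 0.80 × 75 = 60, as stated.

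**Step 2: who is missing.**

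- Decline both aims: 75 − 60 = 15.
- Share of refusers: 15 / 75 = 20%. Share of all offered: 15 / 125 = 12%. The endpoint is about refusers, so 20% is the relevant figure.

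**Step 3: error from using joiners only.** Let J be the share of joiners who give a certain reason and D the share among those who decline both. The share among all refusers is 0.80 J + 0.20 D. The Aim 2-only estimate is J, so its error is J − (0.80 J + 0.20 D) = 0.20 × (J − D).

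| Assumed difference between J and D | Error |
|---|---|
| 10 points | 2 points |
| 20 points | 4 points |
| 30 points | 6 points |
| 40 points | 8 points |

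The documents give no value for the difference. The range is an assumption.

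**Step 4: worst case.** Suppose half of the joiners give the reason (J = 0.50). If none of the 15 give it, the share among all 75 is 0.80 × 0.50 = 40%. If all 15 do, it is 0.40 + 0.20 = 60%. That is 10 points either way and needs a difference of 50 points. The range is always 20 points wide but is symmetric only at one half: at J = 0.70 it runs from 56% to 76%.

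**Step 5: sampling error for comparison.** At n = 60 and a share of 50%, the 95% margin is 1.96 × √(0.25 / 60) = 12.7 points.

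**Step 6: sensitivity to uptake.** The 80% is the plan's assumption. Of 75 refusers, 90% uptake would leave about 8 unobserved (7.5), 70% about 22 (22.5) and 60% would leave 30. These other rates are illustrations.

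**Step 7: with the logs.** For reason and age, the base rises from 60 of 75 to 75 of 75. The margin at 50% falls only from 12.7 to 1.96 × √(0.25 / 75) = 11.3 points. The gain is in coverage more than in precision.

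**The case against.** The case for leaving the plan alone has several parts.

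- *The wording is not exclusive.* Section 4.2.2 says that Aim 2 enrollees will help, which leaves room for other sources. This is true, but no section gives the logs a role in the endpoint, and the only contrast named is Aim 1 against Aim 2.
- *The people at issue are already logged.* The section 5.3 log covers those who decline Aim 2, with their reasons, and the number approached cannot be reported without screening data from the sites. This stands. The information is to be recorded and can be obtained; what is missing is a planned use of it.
- *A reason is not a baseline predictor.* The endpoint rests on clinical and demographic characteristics, and of these the screening log is stated to hold only age, in a population already limited to 75 or older. This stands and limits what the fix can do. A reader might infer that using the log restores the whole secondary endpoint. It does not: NYHA class, LVEF, comorbidity and the other Table 1 variables remain available only for Aim 2 consenters.
- *The error is modest.* At differences of 10 to 40 points it is below the sampling margin. This stands. A reader might infer from the 40% to 60% range that selection bias is as large as sampling error; that range is the extreme case.

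Two further inferences go beyond the documents. One is that Aim 2 overstates device preference. Sections 4.1 and 5.3 make that plausible, but both are expectations, and the direction is not known. The other is that Aim 2 enrollees give a late, post-implant reason while the log holds a contemporaneous one. The window in section 5.3, from implant to 14 days after, governs enrollment and does not say when the refusal reason is elicited. Section 5.4 does not say when the log entry is made.

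**Conclusion.** The concern holds as a gap between the endpoint's target and the data assigned to it. One in five refusers is expected to contribute nothing to the analysis of refusal, although reason and age are to be recorded for them. The likely error in a reason's share is a few points, and its sign cannot be stated in advance. It is still worth correcting, because who refuses and why is what Aim 2 is for, more enrollment would not remove the error, and the data needed are already required.

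The conclusion rests on the plan's 40% and 80% assumptions, on an assumed difference between joiners and decliners, and on the logs being complete. It covers reasons and age only.

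**What to change.** In sections 4.2.2 and 9.1:

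- Tabulate reasons for refusing Aim 1 from the screening log, for all refusers.
- Use the Aim 2 offer log in section 5.3 to identify who joined, and compare reason and age between refusers who joined Aim 2 and those who declined both.
- Report the logged reasons for declining Aim 2.
- State that the clinical predictors of refusal (NYHA class, LVEF, comorbidity and so on) describe only refusers who consented to Aim 2, because the log is not stated to hold them.

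In section 5.4, state that the reason is logged at the time of refusal, and replace transfer on request with routine transfer of the redacted log to the coordinating center.

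Cost: analysis wording plus a small protocol amendment. Section 12.2 requires IRB approval for it, and that review would have to cover sending redacted log data on people who declined both consents. The sites take on routine transfer and must be able to match entries across the two logs. The result is only as good as the completeness of those logs.
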